2.2. Study Objective(s) and Endpoint(s)

[figure not shown]
Objectives	Endpoints
Primary Objectives	Primary Endpoints

 • To evaluate the safety and tolerability of repeat doses of a cream formulation of GSK2646264 in patients with CLE 	
 • Safety and tolerability by laboratory tests, vital signs, 12-lead ECG, and AE reporting.
Secondary Objectives	Secondary Endpoints

 • To determine the effect of GSK2646264 on the reduction in clinical activity score from baseline in treated PV and existing CLE lesions • To evaluate the plasma concentrations of GSK2646264 in patients with CLE • To determine the effect of GSK2646264 on expression of IFN mRNA signature in skin biopsies in treated PV and existing CLE 	
 • Change from baseline of components of a modified RCLASI- composite clinical activity score at day 14 and day 28 in PV and existing lesions in erythema, oedema, dyspigmentation and (scaling in existing CLE lesions only) • PK parameters, including but not limited to AUC, Cmax, tmax, half-life ($t_{1/2}$) if data permits. • Change from baseline in IFN mRNA signature in skin biopsies at day 28 in PV and existing CLE lesions

Objectives	Endpoints
lesions	
Exploratory Objectives	Exploratory Endpoints

 To determine the effect of GSK2646264 on expression of IFN protein markers in skin biopsies in treated PV and existing CLE lesions 	
 Change from baseline in IFN proteins (e.g. MxA, CXCL10) in skin biopsies at day 28 in PV and existing CLE lesions

 To determine the effect of GSK2646264 on expression of pSYK and SYK protein in skin biopsies in treated PV and existing CLE lesions 	
 Change from baseline in pSYK and SYK protein in skin biopsies at day 28 in PV and existing CLE lesions

 To determine the effect of GSK2646264 on immune cell markers in skin biopsies in treated PV and existing CLE lesions 	
 Change from baseline in immune cell proteins (e.g. CD3, CD20, CD11c, CD123, CD68) in skin biopsies at day 28 in PV and existing CLE lesions

 To determine the effect of GSK2646264 on the histological disease activity in PV and existing CLE lesions 	
 Change from baseline in histopathology score (including parakeratosis, ballooning/hydropic degeneration, epidermal cell-death, junctional and dermal inflammation) in skin biopsies at day 28 in PV and existing CLE lesions

 To evaluate the skin concentrations of GSK2646264 in patients with CLE 	
 Skin biopsy concentrations and derived pharmacokinetic parameters of GSK2646264

[figure not shown]
2.3. Study Design

Overview of Study Design and Key Features

Overview of Study Design and Key Features

	
from the first PV. Patients that develop PV lesions at any time during this period, as determined by the local investigative team, will receive 1% strength GSK2646264 on 1 lesion and placebo on 1 lesion daily and either 1% strength GSK2646264 or placebo on an area of uninvolved skin, for skin PK of study drug, for 28 days.
 
 Group B: Patients that have a minimum of 2 active existing CLE lesions as determined by the investigators will be enrolled into group B and have one lesion treated with 1% GSK2646264 and 1 lesion with placebo. 															
Dosing	
 Topical application daily for 28 days 															
Treatment Assignment	
 Group A Subjects will be assigned the following regimens: 
  
 	Skin Sites A/C/D	Sequence assignment ratio	
   
 Sequence 1	A/P/A	4	
 
 Sequence 2	A/P/P	1	
 
 Sequence 3	P/A/A	4	
 
 Sequence 4	P/A/P	1	
  
 
P=Placebo, A= GSK2646264 1% Where sites are highlighted below:
 		Skin Sites A/C/D	Sequence assignment ratio	Sequence 1	A/P/A	4	Sequence 2	A/P/P	1	Sequence 3	P/A/A	4	Sequence 4	P/A/P	1
	Skin Sites A/C/D	Sequence assignment ratio														
Sequence 1	A/P/A	4														
Sequence 2	A/P/P	1														
Sequence 3	P/A/A	4														
Sequence 4	P/A/P	1														

Overview of Study Design and Key Features											

PV lesion and area uninvolved skin (area B and E respectively) will be used solely to take biopsy.
 
 Group B Subjects will be assigned the following regimens: 
  
 	Skin Sites F/ G	Sequence assignment ratio	
   
 Sequence 1	A/P	1	
 
 Sequence 2	P/A	1	
  
 
P=Placebo, A= GSK2646264 1% Where skin sites F and G will be chosen, lesions F> in size than G, and an area of uninvolved skin (area H) will be used solely to take biopsy.
				Skin Sites F/ G	Sequence assignment ratio	Sequence 1	A/P	1	Sequence 2	P/A	1
	Skin Sites F/ G	Sequence assignment ratio									
Sequence 1	A/P	1									
Sequence 2	P/A	1									
Final analysis	
 Final analysis of groups A and B will be reported together after all subjects in groups A (up to 5 subjects) and B (approximately 15 subjects) have completed their follow-up visit. 										

2.4. Statistical Hypotheses

The primary objective of the study is to evaluate the safety and tolerability of repeat doses of a cream formulation of GSK2646264 in patients with CLE. No formal statistical comparisons will be conducted to assess this objective. If deemed appropriate to assess key efficacy and pharmacodynamic endpoints, the following exploratory comparisons may be conducted:

- Group B
 - GSK2646264 treatment vs. Placebo in natural CLE lesions

If deemed appropriate the following exploratory comparisons may be conducted for pharmacodynamic markers from the skin biopsies:

- Group B
 - Baseline GSK2646264 lesion vs uninvolved skin (skin area H)
 - Baseline Placebo lesion vs uninvolved skin (skin area H)
 - GSK2646264 lesion at Day 28 vs uninvolved skin (skin area H)
 - Placebo lesion at Day 28 vs uninvolved skin (skin area H)

3. PLANNED ANALYSES

3.1. Final Analyses

The final planned analyses will be performed after the completion of the following sequential steps:

- All subjects have completed the study as defined in the protocol.
- All required database cleaning activities have been completed and final database release and database freeze has been declared by Data Management.
- All criteria for unblinding the randomisation codes have been met.

4. Randomisation codes have been distributed according to RandAll NG procedures.

4. ANALYSIS POPULATIONS

Population	Definition / Criteria	Analyses Evaluated
Safety	
 • Comprise of all subjects who receive at least one dose of study treatment. • This population will be based on the treatment the subject actually received. 	
 • Study Population • Safety • Efficacy • Pharmacodynamic
Pharmacokinetic	
 • Subjects in the 'Safety' population for whom a pharmacokinetic sample was obtained and analysed. 	
 • PK
PV Failures	
 • Subjects who enrolled into Group A but were not randomised to a treatment. 	
 • AEs relating to PV • Concomitant medications
All Screened	
 • Comprises of all subjects who have entered the study 	
 • Screen failures

NOTES :

- Please refer to [Appendix 8](#): List of Data Displays which details the population to be used for each display being generated.

4.1. Protocol Deviations

- Important protocol deviations (including deviations related to study inclusion/exclusion criteria, conduct of the trial, patient management or patient assessment) will be summarised and listed.
- Protocol deviations will be tracked by the study team throughout the conduct of the study in accordance with the Protocol Deviation Management Plan.
 - Data will be reviewed prior to freezing the database to ensure all important deviations and deviations which may lead to exclusion from the analysis are captured and categorised on the protocol deviations dataset.
 - This dataset will be the basis for the summaries and listings of protocol deviations.
- A separate summary and listing of all inclusion/exclusion criteria deviations will also be provided. This summary will be based on data as recorded on the inclusion/exclusion page of the eCRF.

5. CONSIDERATIONS FOR DATA ANALYSES AND DATA HANDLING CONVENTIONS

Table 1 provides an overview of appendices within the RAP for outlining general considerations for data analyses and data handling conventions.

Table 1 Overview of Appendices

Section	Component
11.1	Appendix 1 : Time & Events
11.2	Appendix 2 : Data Display Standards & Handling Conventions
11.3	Appendix 3 : Derived and Transformed Data
11.4	Appendix 4 : Premature Withdrawals & Handling of Missing Data
11.5	Appendix 5 : Values of Potential Clinical Importance
11.6	Appendix 6 : Model Checking and Diagnostics for Statistical Analyses.

6. STUDY POPULATION ANALYSES

6.1. Overview of Planned Analyses

The study population analyses will be based on the Safety population, unless otherwise specified.

Table 2 provides an overview of the planned study population analyses, with full details of data displays being presented in [Appendix 8](#): List of Data Displays.

Table 2 Overview of Planned Study Population Analyses

Endpoint / Parameter / Display Type	Data Displays Generated		
	Table	Figure	Listing
Subject Disposition			
Subject Disposition	Y		
Reasons for Screen Failure	Y		Y
Subjects by Country and Centre	Y		
Reasons for Subject Withdrawal			Y
Subjects for Whom the Treatment Blind was Broken			Y
Planned and Actual Treatments			Y
Protocol Deviations			
Important Protocol Deviations	Y		Y
Subjects with Inclusion/Exclusion Criteria Deviations			Y [1]
Populations Analysed			
Study Populations and Exclusions	Y		
Subjects Excluded from Any Population			Y
Demographic and Baseline Characteristics			
Demographic Characteristics	Y		Y
Race and Racial Combinations	Y		Y [2]
Race and Racial Combination Details	Y		
Prior and Concomitant Medications			
Current/Past Medical Conditions	Y		Y
Concomitant Medications	Y		Y
Type of CLE	Y		Y
Exposure and Treatment Compliance			
Exposure to Study Treatment	Y		Y

NOTES :

- Y = Yes display generated.

[1] Listing also includes analysis population exclusions.

[2] Listing of race.

7. PRIMARY STATISTICAL ANALYSES

7.1. Safety Analyses

7.1.1. Overview of Planned Adverse Events Analyses

The safety analyses will be based on the Safety population, unless otherwise specified.

Table 3 provides an overview of the planned analyses, with full details of data displays being presented in [Appendix 8: List of Data Displays](#).

Table 3 Overview of Planned Adverse Events Analyses

Endpoint / Parameter/ Display Type	Absolute		
	Summary		Individual
	T	F	L
Adverse Events (AEs)			
All AEs by SOC	Y		Y
All Drug-Related AEs by SOC	Y		
Subject Numbers for Individual AEs			Y
Relationship Between AE SOCs, PT & Verbatim Text			Y
Serious and Other Significant AEs			
Non-Fatal Serious AEs			Y
Serious AEs by SOC	Y		
Reasons for Considering as a Serious AE			Y
AEs Leading to Withdrawal from Study / Permanent Discontinuation of Study Treatment by Overall Frequency	Y		Y

[1] Plot of common AEs and relative risk will be generated.

7.1.2. Overview of Planned Clinical Laboratory Analyses

The safety analyses will be based on the safety population, unless otherwise specified.

[Table 4](#) provides an overview of the planned analyses, with further details of data displays being presented in [Appendix 8: List of Data Displays](#).

Table 4 Overview of Planned Clinical Laboratory Analyses

Endpoint / Parameter/ Display Type	Absolute		Change from BL	
	Summary	Individual	Summary	Individual
	T	L	T	L
Chemistry				
Chemistry Changes from Baseline			Y	
Emergent Chemistry Results Relative to Normal Range	Y			
Hematology				
Hematology Changes from Baseline			Y	
Emergent Hematology Results Relative to Normal Range	Y			
Urinalysis				
Urine Concentration Changes from Baseline			Y	
Emergent Urinalysis Dipstick Results	Y			
Hepatobiliary (Liver)				
Liver Monitoring/Stopping Event Reporting	Y			
Hepatobiliary Laboratory Abnormalities	Y			
Medical Conditions for Subjects with Liver Stopping Events		Y		
Substance Use for Subjects with Liver Stopping Events		Y		
All Laboratory				
Laboratory Data for Subjects with Abnormalities of Potential Clinical Concern		Y		Y
Laboratory Data Abnormalities of Potential Clinical Importance		Y		Y

NOTES:

- T = Table, L = Listings, Y = Yes display generated, PCI = Potential Clinical Importance, BL = Baseline
- Summary = Represents TFL related to any summaries (i.e. descriptive statistics) of the observed raw data.
- Individual = Represents FL related to any displays of individual subject observed raw data.

7.1.3. Overview of Planned Other Safety Analyses

The safety analyses will be based on the Safety population, unless otherwise specified.

[Table 5](#) provides an overview of the planned analyses, with further details of data displays being presented in [Appendix 8: List of Data Displays](#).

Table 5 Overview of Planned Other Safety Analyses

Endpoint / Parameter/ Display Type	Absolute		Change from BL	
	Summary	Individual	Summary	Individual
	T	L	T	L
ECG				
ECG Findings	Y			
Maximum Emergent QTc Values by Category	Y			
Change from Baseline in ECG Values by Visit			Y	
Maximum Change from Baseline in QTc Values by Category			Y	
All ECG Values for Subjects with a Value of PCI		Y		Y
ECG Values of PCI		Y		Y
Abnormal ECG Findings		Y		
Vital Signs				
Change From Baseline in Vital Signs by Visit			Y	
Emergent Vital Signs Results by Grade Relative to Normal Range by PCI Criteria	Y			
All Vital Signs for Subjects with Values of PCI		Y		Y
Local Tolerability				
Skin Irritation Score ¹	Y ²	Y ²	Y ²	Y ²
Dermal Response and Other Dermal Effects	Y	Y		

NOTES:

- T = Table, L = Listings, Y = Yes display generated, PCI = Potential Clinical Importance, BL = Baseline
- Summary = Represents TFL related to any summaries (i.e. descriptive statistics) of the observed raw data.
- Individual = Represents FL related to any displays of individual subject observed raw data.
- [1]: See Section 11.3.3 for more details.
- [2]: Absolute and change from baseline will be displayed on the same output.

8. SECONDARY STATISTICAL ANALYSES

8.1. Efficacy Analyses

8.1.1. Overview of Planned Efficacy Analyses

The secondary efficacy analyses will be based on the safety population, unless otherwise specified and will be based on Group B subjects only.

[Table 6](#) provides an overview of the planned efficacy analyses, with further details of data displays being presented in [Appendix 8: List of Data Displays](#).

Table 6 Overview of Planned Efficacy Analyses

Endpoint	Absolute			
	Summary		Individual	
	T	F	F	L
Clinical Score				
RCLASI and Components	Y ^{1,2}	Y ²	Y ²	Y ¹

NOTES :

- T = Table, F = Figure, L = Listing, Y = Yes display generated.
- Stats Analysis = Represents TFL related to any formal statistical analyses (i.e. modelling) conducted.
- Summary = Represents TFL related to any summaries (i.e. descriptive statistics) of the observed raw data.
- Individual = Represents FL related to any displays of individual subject observed raw data.
- [1]: Include both absolute and change from baseline
- [2]: By Disease Characteristics (Chronic CLE, Acute CLE, Sub-acute CLE, LET and All).

8.1.2. Planned Efficacy Statistical Analyses

Due to the small number of patients in the study, no formal statistical analysis will be conducted.

8.2. Pharmacokinetic Analyses

8.2.1. Overview of Planned Pharmacokinetic Analyses

The pharmacokinetic (PK) analyses will be based on the Pharmacokinetic population, unless otherwise specified and will be based on Group B subjects only.

The pharmacokinetic analyses will be performed by, or under the direct auspices of Clinical Pharmacokinetic Modelling Simulation (CPMS), GlaxoSmithKline.

[Table 7](#) provides an overview of the planned analyses, with full details being presented in [Appendix 8: List of Data Displays](#).

Table 7 Overview of Planned Pharmacokinetic Analyses

Endpoint	Untransformed				Log-Transformed	
	Summary		Individual			
	T	F	F	L		
Plasma						
Plasma concentrations	Y	Y ^[1,2]	Y ^[1]	Y		
Plasma PK Parameters ^[3]	Y			Y	Y	

NOTES :

- T = Table, F = Figure, L = Listings, Y = Display generated.
- Stats Analysis = Represents TFL related to any formal statistical analyses (i.e. modelling) conducted.
- Summary = Represents TFL related to any summaries (i.e. descriptive statistics) of the observed raw data.
- Individual = Represents FL related to any displays of individual subject observed raw data.
- [1] Linear and Semi-log plots will be created on the same display
- [2] Separate Mean (\pm SD) and Median (range) plots will be generated
- [3] if data permit

8.2.2. Drug Concentration Measures

Refer to [Appendix 5: Data Display Standards & Handling Conventions](#) (Section [11.2.3 Reporting Process & Standards](#)).

8.2.3. Pharmacokinetic Parameters

8.2.3.1. Deriving Pharmacokinetic Parameters

- Refer to [Appendix 5: Data Display Standards & Handling Conventions](#) (Section [11.2.3 Reporting Process & Standards](#)).
- The pharmacokinetic parameters will be calculated by standard non-compartmental analysis according to current working practices and using WinNonLin, if data permit.
- All calculations of non-compartmental parameters will be based on actual sampling times.

Table 8 Derived Pharmacokinetic Parameters

Parameter	Parameter Description
AUC(0-t)	Area under the concentration-time curve from time zero to the time of the last quantifiable concentration (C(t)) will be calculated using the linear trapezoidal rule for each incremental trapezoid and the log trapezoidal rule for each decremental trapezoid.
AUC(0-∞)	Area under the concentration-time curve extrapolated to infinity will be calculated as: $\text{AUC} = \text{AUC}(0-t) + C(t) / \text{lambda}_z$
%AUCex	The percentage of AUC (0-∞) obtained by extrapolation (%AUCex) will be calculated as: $[\text{AUC}(0-\text{inf}) - \text{AUC}(0-t)] / \text{AUC}(0-\text{inf}) \times 100$
Cmax	Maximum observed concentration, determined directly from the concentration-time data.
t _{max}	Time to reach Cmax, determined directly from the concentration-time data.
t _{1/2}	Apparent terminal half-life will be calculated as: $t_{1/2} = \ln 2 / \text{lambda}_z$

NOTES:

- Additional parameters may be included as required.
- Lambda_z is the terminal phase rate constant.

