### **9.4. Key Elements of Analysis Plan**

Data will be summarized and analysed according to the GSK reporting standards, where applicable. Complete details will be documented in the RAP. Any deviations from, or additions to, the original analysis plan described in this protocol will be documented in the RAP.

Final analysis of groups A and B will be reported together after all subjects in groups A (up to 5 subjects) and B (approximately 15 subjects) have completed their follow-up visit.

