#### **9.4.2. Secondary Analyses**

All plasma GSK2646264 concentration data will be graphically represented, descriptively summarised and listed appropriately. Plasma GSK2646264 concentration time data will be analysed using a population pharmacokinetics (PK) model developed previously using data from study 200196 (FTIH of GSK2646264). Population PK parameters (Cmax, AUC(0- $\tau$ ) and terminal phase half life (t1/2) will be reported. Pharmacokinetic data will be presented in graphical and/or tabular form and will be summarized descriptively. All pharmacokinetic data will be stored in the Archives, GlaxoSmithKline Pharmaceuticals, R&D.

Descriptive statistics of both raw and change from baseline, where appropriate, (i.e. n, arithmetic mean, standard deviation, minimum, median and maximum) will be calculated

for erythema, oedema, dyspigmentation (and scaling in existing lesions only) and modified RCLASI and summarized study part. All data will be listed.

Change from baseline in each clinical activity assessment will be analysed for each lesion type using a mixed effects model fitting visit, treatment and lesion location as fixed effects and subject as random. Estimates of the differences between GSK2646264 and placebo will be calculated and appropriate statistical inferences based on these results will be made.

Descriptive statistics of both raw and change from baseline data, where appropriate, (i.e. n, arithmetic mean, standard deviation, minimum, median and maximum) will be calculated for the IFN mRNA endpoints and summarized by lesion type (PV and natural lesions). All data will be listed.

If data permits, formal statistical analyses of the IFN mRNA endpoints may be conducted.

Change from baseline in each IFN mRNA signature endpoints will be analyzed by study part using a mixed model including treatment and lesion number as fixed effects and subject as a random effect. Estimates of the treatment means and differences will be presented with the associated 95% confidence intervals. Distributional assumptions underlying the analyses will be assessed as appropriate. If these assumptions are strongly violated, appropriate transformations will be investigated and if required alternative statistical analyses considered.

Full details will be provided in the RAP.

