Secondary Analyses	
 All plasma GSK2646264 concentration data will be graphically represented, descriptively summarised and listed appropriately. Plasma GSK2646264 concentration time data will be analysed using a Non-compartmental Analysis (NCA), if data permit. Pharmacokinetic data will be presented in graphical and/or tabular form and will be summarized descriptively. Descriptive statistics of both raw and change from baseline, where appropriate will be calculated for erythema, oedema, dyspigmentation (and scaling in existing lesions only) and modified RCLASI. Change from baseline in each clinical activity assessment will be analysed using a repeated measures mixed effects model with subject random effect and treatment and baseline activity score as the fixed effect. IFN mRNA data will be normalised, back transformed and log2 transformed mRNA intensity data in each IFN mRNA signature endpoints will be analysed using a mixed model with subject random effect and treatment and baseline intensity as the fixed effect. Fold changes will be derived from the back-transformed estimate of the difference between adjusted means.
Exploratory Analyses	
 Descriptive statistics of both raw and change from baseline will be calculated for exploratory Pharmacodynamic/Biomarker endpoints. Change from baseline in these endpoints may be analysed using a mixed model with subject random effect and treatment and baseline activity score as the fixed effect. If data permits, endpoints may be analysed using a mixed model with subject random effect and skin type as the fixed effect to study the difference due to skin type.

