2. SUMMARY OF KEY PROTOCOL INFORMATION

2.1. Changes to the Protocol Defined Statistical Analysis Plan

The following changes were made to the originally planned statistical analysis specified in the protocol amendment 3 [(Dated: 14/DEC/2017)]:

- The secondary endpoint for the plasma concentration of GSK2646264 is clarified in the RAP:

Secondary Objectives	Secondary Endpoints

 • To evaluate the plasma concentrations of GSK2646264 in patients with CLE 	
 • PK parameters, including but not limited to AUC, Cmax, tmax, half-life ($t_{1/2}$) if data permits.

Since no subjects were randomised into Group A, no outputs will be generated for this part. Listings will be produced for the enrolled (PV failure) subjects in Group A who were not randomised.

[figure not shown]
In the protocol Section 9.4.2, it states that 'Change from baseline in each clinical activity assessment will be analysed for each lesions type'. Due to the small number of patients in the study, no formal statistical analysis will be conducted for the RCLASI scores. Descriptive summary for raw and change baseline scores will be calculated and presented.

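### The SAP replaces the protocol's population PK analysis with non-compartmental analysis of samples too sparse for it, without listing or justifying the change, and defines no time zero or dosing interval for AUC and tmax

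*SAP*

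**What the plan says.** Protocol 9.4.2 says plasma concentration-time data "will be analysed using a population pharmacokinetics (PK) model developed previously using data from study 200196", the first-time-in-human study, and that Cmax, AUC(0-tau) and terminal half-life will be reported. Protocol 9.4 adds: "Any deviations from, or additions to, the original analysis plan described in this protocol will be documented in the RAP".

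The SAP synopsis says: "Plasma GSK2646264 concentration time data will be analysed using a Non-compartmental Analysis (NCA), if data permit". SAP 8.2.3.1 repeats this: "The pharmacokinetic parameters will be calculated by standard non-compartmental analysis according to current working practices and using WinNonLin, if data permit". No population PK analysis appears anywhere in the SAP.

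SAP 2.1 opens with "The following changes were made to the originally planned statistical analysis specified in the protocol amendment 3". Its only PK entry is "The secondary endpoint for the plasma concentration of GSK2646264 is clarified in the RAP", followed by AUC, Cmax, tmax and half-life. It does not mention the method.

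SAP Table 8 lists AUC(0-t), AUC(0-inf), %AUCex, Cmax, tmax and half-life. AUC(0-t) is "Area under the concentration-time curve from time zero to the time of the last quantifiable concentration", with no dose or day named. AUC(0-tau) is not listed, although a note allows that "Additional parameters may be included as required".

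**The concern.** Sparse samples taken over weeks of daily dosing, with the time since the last dose recorded, suit a population model. Non-compartmental analysis (NCA) needs several samples within a defined interval. The SAP keeps the sparse schedule and drops the method that could use it.

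PK parameters are the endpoint of a secondary objective. SAP Tables 4.2 and 4.3 and Listing 38 could be empty. If filled, they could hold AUC and tmax values whose meaning depends on an unstated origin. A reader would naturally set such an AUC beside the predicted daily exposure in protocol 4.5, and the two would not be the same quantity.

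**Working it through.** **1. Samples.** From the Group B time and events table (protocol 7.1.3, SAP 11.1.4): Day 1 pre-dose and 5 h (2), Days 2-13 (1), Day 14 pre-dose (1), Days 21-27 (1), Day 28 post-dose (1), Days 29-42 (1), follow-up in Days 43-56 (1). The total is 2+1+1+1+1+1+1 = 8, and one of these precedes any drug.

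**2. Samples within one dosing interval.** No steady-state interval is profiled. Two samples share one only by chance of visit day:
- a Day 13 post-dose sample with Day 14 pre-dose (1 of the 12 days allowed in Days 2-13);
- Day 28 post-dose with a Day 29 sample (1 of the 14 days allowed in Days 29-42).

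A Day 2 pre-dose sample would join the two Day 1 samples at 0, 5 and 24 h, but that covers the first dose only.

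**3. Time zero.** Three conventions bear on it, and none settles it. SAP 11.2.2.1 makes Day 1 the plasma PK baseline, the schedule records time since the last dose, and SAP 11.2.3 refers to time relative to dosing without saying which dose.

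**4. The reference figure.** Protocol 4.5 predicts Cmax 0.780 ng/mL and steady-state AUC(0-24) 17.2 ng.h/mL. These cannot be re-derived, because the model parameters are not given. They are coherent: 17.2/24 = 0.717 ng/mL on average, below 0.780.

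**5. Scale from document figures alone.** If kinetics are linear and constant over time, the total AUC after 28 doses is 28 × 17.2 = 481.6 ng.h/mL, against 17.2 for one day.

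**6. Illustration under an assumed model.** One compartment, first-order absorption, 28 daily doses:

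C(t) = Σ 17.2 × ka·ke/(ka − ke) × [exp(−ke·s) − exp(−ka·s)], summed over doses already given, where s is the time since each dose and ke = ln 2 / half-life.

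For each assumed ka, the half-life is solved so that steady-state Cmax = 0.780. SAP Table 8's linear-up, log-down rule is then applied to the eight samples. Visit days vary over their windows, the Day 2-13 and Day 21-27 samples are pre-dose or at 5 h, and the Day 28 sample is at 1, 4 or 8 h. For the last-dose reading, the time-zero value is set to 0 or to the true trough.

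| ka (/h) | Half-life (h) | AUC(0-t)/17.2, first dose | AUC(0-t)/17.2, last dose |
|---|---|---|---|
| 0.1 | 18.3 | 20.7-27.0 | 1.09-1.91 |
| 0.15 | 26.3 | 21.2-27.3 | 1.55-2.31 |
| 0.2 | 33.0 | 21.4-27.5 | 1.97-2.67 |
| 0.3 | 43.5 | 21.9-27.9 | 2.63-3.24 |
| 0.5 | 56.5 | 22.5-28.2 | 3.46-3.97 |
| 1 | 71.0 | 23.2-28.2 | 4.40-4.80 |
| 2 | 81.0 | 23.6-28.1 | 4.99-5.36 |

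A second set of assumptions (half-life 12-168 h, absorption half-life 6 h, quantification limit 0.001 or 0.05 ng/mL, Day 28 sample at 4 h) gives 325-452 ng.h/mL from the first dose: 325/17.2 = 19 to 452/17.2 = 26 times.

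**7. Other quantities in the step 6 model.**
- tmax from the first dose, with Day 28 sampled at 4 h: 101-652 h, against 1.9-8.9 h within a dosing interval.
- Observed Cmax, with Day 28 sampled at 4 h: 94%-100% of true.
- AUC from the Day 1/Day 2 set: about 16%-34% of the steady-state daily AUC.
- AUC(0-tau) from a chance pair, assuming the starting trough equals the ending one: 0.915-0.965 of true (Day 13 at 5 h with Day 14) or 0.932-0.987 (Day 28 at 4 h with Day 29 at 24 h).

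**The case against.** **The change is disclosed.** Protocol 9.4 asks only for documentation in the RAP and names neither section 2.1 nor a justification. NCA is stated twice in the SAP. A reader might infer a concealed change, and the documents do not support that. What stands is that the section presented as the list of changes omits this one. The same section does give a reason for dropping the RCLASI model.

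**The 28-dose AUC is only one reading.** A reader might infer that the SAP commits to it. It does not. The other AUC intervals in the documents are one day or one dosing interval, samples are timed from the last dose, and the reference to current working practices may narrow the calculation. But the SAP does not state the restriction, and counting from the last dose gives no time-zero sample and includes the washout.

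**The condition on the data already covers sparse sampling.** If it is not met, concentrations alone are reported, which is a defensible result. Even so, the secondary endpoint then has no parameters, when the protocol's method could have used the same samples.

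**More data may exist.** Protocol 7.5.1 permits extra samples and Table 8 permits extra parameters. Neither is planned.

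**Exposure can still be compared roughly.** In the assumed model, the Day 28 concentration at 4 h times 24 is 103%-109% of 17.2, and the Day 14 pre-dose concentration times 24 is 84%-86%. So it would be wrong to infer that all comparison with predicted exposure is lost. The Table 8 AUCs are what cannot be compared.

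**The magnitudes are soft.** The absorption rates are assumed, the table applies no quantification limit, and the predicted Cmax is taken to be at steady state. Calibrating to 0.76 or 0.80 instead of 0.78 moves the half-life from 18.3 h to 26.7 or 14.0 h (ka 0.1), and from 81 h to 118 or 62 h (ka 2). The ranges show scale and are not predictions.

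**Conclusion.** The concern holds, and it should be fixed. The method change, its absence from SAP 2.1, the missing AUC(0-tau) and the undefined time zero can be read directly from the documents. So can the lack of a profiled steady-state interval. None of these depends on a model.

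Followed as written, the SAP gives either no PK parameters or AUC and tmax values that are not steady-state daily exposure. The size of the mismatch (roughly 20 to 28 times from the first dose, 1 to 5 times from the last) is an illustration resting on an assumed one-compartment model.

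The reach is limited. Concentration tables and plots, observed Cmax (nearly) and the in-study exposure rule in protocol 5.4.3 are unaffected, and the primary safety endpoint is not involved. Whether a half-life can be estimated depends on an assay limit that the documents do not state.

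**What to change.** Restore the protocol 9.4.2 analysis: fit the existing population model using actual sample times and report Cmax, AUC(0-tau) and half-life. Remove AUC(0-t), AUC(0-inf), %AUCex and tmax from Table 8, and amend the endpoint wording in SAP 2.1 and 2.2, which names tmax, to match. Keep the descriptive concentration summaries.

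If the model is not used, list and justify the change in SAP 2.1 and report observed concentrations. Derive an NCA parameter only for a stated dose, time zero and dosing interval (AUC(0-tau)), in subjects with enough samples in that interval.

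The first option costs modelling time and SAP wording, with no new samples. Its estimates would partly borrow from 20 earlier-study subjects (17 healthy volunteers, 3 with cold urticaria). The healthy-volunteer data came from 5.2%-10.2% of body surface area over up to 4 days, against about 0.5% for 28 days here: 5.2/0.5 = 10.4 and 10.2/0.5 = 20.4, so roughly 10 to 20 times the treated area. The report should state this. The second option costs only wording, but leaves few or no subjects with an AUC.
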